5 STUDY INTERVENTIONS

5.1 Interventions, Administration, and Duration

The M&M personalized music program will be implemented for at least 8 months in each intervention facility. (Obviously, facilities are encouraged to continue to use the music devices with patients long after this 8-month period and the devices will remain at the facility for use among appropriate patients). The intervention consists of: 1) identifying the music a resident with ADRD preferred when she was between the ages of 18 and 24, either by consulting family members or through trial and error; 2) creating a personalized playlist for each resident; 3) loading this personalized playlist on the resident's music player (iPod); and 4) using the iPod with the resident twice a day for approximately 30 minutes to 1 hour per use, at times when residents with ADRD tend to experience BPSD. Recommended times are when the resident gets up in the morning (during daily personal care) and in the late afternoon, when sundowning is common. In addition to these set times, NH staff are encouraged to use the music at other times when an individual resident is likely to experience BPSDs. In the first parallel trial. NH staff will be responsible for completing all four steps. In the second parallel trial. research staff will create personalized playlists (step 2) and load music players (step 3). For the second parallel trial, staff will provide Brown with 15 eligible residents' "preferred" music genre and resident age. Brown research staff will preload iPods with popular music in the resident's preferred genre from when they were between the ages of 16 and 26 (current best practice recommendation). This process is similar to playlists generated by Spotify and other streaming services. Additionally, we will be using playlists from the first trial to culturally and regionally tailor music selections. This is particularly important for the current study as we have four regionally and racially diverse corporations: two NH corporations serving predominately white, rural

residents in the Midwest, one NH corporation serving mostly African American residents in the DC metro area; and one NH corporation serving southern African American and white residents. Based on our extensive population experience and large music database from the R21 and R33 phases we are able to observe differences in music preferences between a majority African American NH in rural Georgia and a majority African American NH in rural Georgia and a majority African American NH in urban Maryland. Approximately 15% of all NH residents are African American; approximately 25% of the study sample is African American. This over-representation allows for cultural and regional tailoring of music playlists and has implications for the uptake of the Music & Memory program beyond the current study. By preloading devices with music, the program can be led by nursing staff from the beginning (step 4). We will compare the effects of these two processes on targeted use of the music to address clinical agitation.

In our preliminary work, funded by the Research and Retirement Foundation, Brown (in partnership with B&F Consulting) identified facilitators and barriers to implementing the M&M program in six, high-performing NHs in the northeast. Important findings from this preliminary work include the need to: align the intervention to priorities of individual facilities; pilot the intervention with a few residents before expanding to an entire unit or NH; and integrate M&M into routine care planning and quality improvement activities to sustain use. During the R21, Brown and B&F translated these lessons learned into a step-by-step Implementation Guide (Appendix A). The Implementation Guide addresses logistics and process steps, including:

- Identifying a computer to house an iTunes library,
- Charging and storing iPods,
- Researching resident playlist preferences,
- Downloading personalized playlists,
- Piloting the intervention with the first resident,
- Scaling the intervention across a unit / within a nursing home,
- · Incorporating the intervention into care planning and data tracking, and
- Sustaining the program after the 8-month intervention period.

The Implementation Guide also provides checklists for tracking monthly progress towards successful implementation.

Each participating NH receives two types of intervention trainings. First, NH staff will participate in standard M&M training and certification. Standard M&M training and certification is offered as a two, 1.5-hour live webinars, covering the benefits of M&M and a basic introduction to the equipment. After completing these two webinars, NHs become certified in M&M and receive a certificate to display in their facility.

The second intervention training will be administered by the corporations for their participating facilities. This training will follow the steps outlined in the Implementation Guide. During the R33, B&F consulting will train and mentor corporate trainers in how to introduce and then disseminate M&M. This pragmatic approach mimics real-world diffusion and allows us to efficiently deliver the intervention to the 27 treatment NHs in each trial. In keeping with a pragmatic trial, implementation will be tailored to the needs of individual corporations and their facilities. However, at a minimum, corporate trainers will lead monthly coaching calls with the project team in the intervention facilities to track progress and set goals. Corporate trainers will help identify the "right" NH staff to participate in each NH's M&M team and will mentor teams throughout the process, helping them to: set milestones, identify and track process data, review progress, and make mid-course corrections. The project team must include: the NH administrator, DON, activities staff, a nurse manager, and a certified nursing assistant. Other team members may be added, as appropriate. Corporate trainers will visit each NH at least twice during the intervention (launch and mid-implementation) to provide technical assistance and support.

The research team has established serval ways to monitor adherence to the intervention protocol which are described in 9.4.3 Process Measures for Implementation Analysis.

5.2 Concomitant Interventions

Many eligible facilities are likely to have periodic, or even daily, music-based activities for residents. Facilities may also be testing other non-pharmaceutical options for addressing BPSD in ADRD while participating in the current study. However, facilities that are already systematically using personalized music, delivered through headphones or personal speakers, with multiple residents (whether M&M certified or not) will be excluded from the current study.

6 DATA SOURCES AND ELEMENTS

We seek to assess the effect of M&M on agitated and aggressive behaviors in NH residents with moderate to severe dementia. Agitated and/or aggressive behaviors are measured three ways: by interviewing staff about resident behaviors over time (primary outcome); through direct observation of residents when using and not using M&M (secondary outcome); and using available administrative data (secondary outcome). Other secondary outcomes include: other emotional states directly observed while the resident is using and not using M&M (anger, pleasure, alertness, sadness), antipsychotic use, antidepressant use, anxiolytic use, and depression. We would also like to understand best practices for integrating the Music and Memory program into existing care processes, facilitators and barriers of using the music, and how the intervention is implemented for each eligible patient (e.g. dose, reason for use, time of day) that might contribute or detract from its effectiveness.

6.1 Data Sources

Secondary Data

Electronic Health Records (EHRs): Three of our partners use PointClickCare (PCC); the other, has two vendors AmeriTec and Matrix Care. We are currently working with these EHR vendors on the PROVEN trial. Thus, we already have procedures in place to extract and link these EHR data with national Medicare repository data and ultimately to Medicare enrollment records. We will use the NHs' EHR to obtain "real-time," individual patient-level data for MDS assessments, user-defined assessments (UDAs), and medication order data.

Minimum Data Set (MDS): The MDS has nearly 400 data elements, including cognitive function, communication / hearing problems, physical functioning, behavioral problems, continence, mood state, diagnoses, health conditions, special treatments, and medication use. Staff complete assessments for *all* individuals admitted to Medicare and Medicaid-certified NHs, including enrollees in both traditional Medicare and Medicare Advantage. Staff are required to submit MDS data to CMS regularly(66-69) and complete assessments upon admission, quarterly, and with changes in status or transfer from the building. Repeated evaluations of the reliability of the MDS reveal adequate to good values on most data items and scales. Brown investigators found that missing data are scarce.(66-69) Research using MDS data has made major contributions to our understanding of how policy, fiscal, and clinical factors influence the quality of NH care,(68, 70-80) and much of this work has been conducted by Brown investigators participating in this proposed project.

Medicare Enrollment, Vital Status, and Chronic Condition Warehouse Data: Brown investigators have decades of experience working with Medicare files linked to MDS and provider-specific data. The Medicare enrollment file provides demographic information as well as Medicaid eligibility, HMO status, and mortality data. The Chronic Condition Warehouse data elements include a summary of the past presence of over 20 unique diagnoses present on any Medicare claim. Because we will obtain real-time MDS data from the facilities, we will also request the quarterly updates to the Vital Status and Chronic Condition Warehouse file from CMS; this will allow us earlier access to date of death than the enrollment file. These data allow us to track mortality even in the event that a resident is hospitalized and does not return to their original NH.

Certification and Survey Provider Enhanced Reporting (CASPER): CASPER are publicly-available data from the Medicare/Medicaid certification and inspection process that all NHs undergo. Brown investigators have assembled a three-decade data panel on all certified U.S. facilities including data on ownership, size, staffing, services, patient acuity, and quality inspection results.(81, 82)

Primary Data

Primary data collection tools can be found in Appendices B-H. These data will be collected by independent data collectors during three site visits (baseline, four, and eight months).

iPod Metadata: The iPod shuffle retains limited data about use. Information about the songs played (e.g., artist, album, track title, duration of track, genre) and the number of times a song is played are available and will be downloaded.

Staff Interviews: the RAs will interview the NH caregiver most familiar with the resident using the Cohen Mansfield Agitation Inventory (CMAI), a validated 29-item tool for measuring agitation in people with ADRD living in NHs.(83, 84) We will use the CMAI to assess the frequency and severity of eligible residents' behaviors over the previous week.

Resident Observation (Trial 1 Only): The Agitated Behaviors Mapping Instrument (ABMI) will be used to observe resident behaviors at the point of intervention. Using independent, trained observers, we will observe

the frequency of residents' agitated behaviors over short intervals, when they are using and not using the M&M intervention. We will also use the Lawton Observed Emotion Rating Scale (OERS),(85) which was designed to measure pleasure, anger, anxiety/fear, sadness, and general alertness. Reactions to music will be captured, when observations include the use of M&M.

Implementation Observation Checklist: The Implementation Observation Checklist is completed by data collectors while on-site. It describes adherence to specific aspects of the study protocol (e.g., are the playlists individualized, are the iPods labeled, are frontline staff involved in delivering intervention to residents, etc).

Key Informant Interviews: Key informant interviews with the administrator and nursing lead in each intervention facility will be completed by Brown research team members at 4- and 8-months (mid- and full-implementation). These interviews will identify facilitators, barriers, and best-practices related to implementing the M&M program, and feedback on corporate trainings.

6.2 Data Linkages

During the R21, we developed and tested procedures for linking primary data, collected on-site at the nursing homes, to existing secondary data sources at the resident-level (Figure 2). Data linkage techniques are described in the paragraphs below.

[figure not shown]

Figure 3. Linking Primary and Secondary Data at the Resident-Level

As described in Section 6.1 Data Sources, there are four types of data that will be collected on-site: staff interview, resident observation, implementation observation, and iPod metadata. These data will be linked to secondary data obtained directly from NHs (MDS, UDA, and medication order data) and secondary data obtained directly from CMS (Medicare Enrollment, Vital Status, Chronic Condition Warehouse Data, and Certification and Survey Provider Enhanced Reporting). Data collected on-site will be entered using tablets through data entry systems developed in Qualtrics, the secure web-based survey tool supported by Brown's Computing & Information Services. Data will be uploaded to the Qualtrics central servers using a secure channel. When entering the study data in Qualtrics, the patient data will only be identified by a pre-assigned Brown study ID; no personally identifying information (PII) or existing IDs (e.g., medical record number, social security number) will be entered. In preparation for analyses, the primary data will be downloaded from Qualtrics and stored on a secure server at Brown. Using a secure crosswalk of Brown study IDs to real person identifiers, the primary data will be linked to the secondary data (the collection of which was already approved by the IRB) for analyses. All analytic files released by the Systems Manager to analysts will be stripped of PII and will include only the Brown study ID.

Brown University investigators and database management staff already receive national MDS, Medicare, and CASPER data semi-annually or quarterly under several CMS data use agreements (DUAs). There is a well-established database management structure for linking these files. Brown University also has experience

integrating EMR data from with CMS Medicare enrollment records and Medicare claims. Using algorithms based on standard patient identifiers including Heath Insurance Claim (HIC) numbers, date of birth, gender, and Social Security Numbers (SSNs), matching rates generally exceed 98%. The new activity for METRICAL is linking primary data collected on-site to secondary data. In the R21 pilot study, secure data transfer and linkage of primary and secondary data for all four corporations were successfully accomplished.

7 SAFETY ASSESSMENTS

7.1. Minimal Risk Determination:

There are special informed consent considerations for individual residents in the study. The intervention is of relatively low risk, and it will be implemented facility-wide as part of the intervention facilities' standard operating procedures for addressing agitated and aggressive behaviors in dementia. Thus, we received a waiver of individual informed consent as set forth by the four criteria found in HHS 45 CFR 46:116 (Brown University IRB #1705001793):

- 1. The research involves no more than minimal risk;
- 2. The waiver will not adversely affect the rights and welfare of the subjects we are merely asking the staff about resident behaviors and observing residents from afar with no direct contact;
- 3. The research could not practicably be carried out without the waiver this study involves evaluative measures of different types (observations, metadata from the music device, and MDS assessments) which need to be linked but are individually otherwise exempt or, due to their unobtrusive nature, readily waiver consent. These secure data linkages, necessary for the full evaluation, would not be possible without a waiver of individual consent; and
- 4. Whenever appropriate, subjects will be provided with additional pertinent information after participation

7.2. Serious Negative Reactions and Serious Adverse Events

Please refer to the Data Safety and Monitoring Plan and Data Safety Monitoring Board Charter for complete safety assessment information.

Adverse Events: An adverse event (AE) is any untoward or unfavorable medical occurrence in a human study participant, including any abnormal sign (e.g. abnormal physical exam or laboratory finding), symptom, or disease, temporally associated with the participants' involvement in the research, whether or not considered related to participation in the research. The potential AEs that could occur during this trial are: distress or strong negative emotional reactions in response to listening to the music delivered via the M&M intervention; and distress or strong negative emotional reactions in response to being observed (Trial 1 Only). Distress or strong negative emotional reactions to the music may include screaming / calling out, crying (not always a negative response), or attempting to remove headphones. Distress or strong negative emotional reactions to being observed may include screaming or becoming agitated / aggressive. Distress resulting from the music and the distress of being observed by a data collector would be classified as mild because the distress is easily tolerated and/or remediated, requires no medical evaluation, and has signs and symptoms that are transient. An immediate, negative reaction to the music would fit the study relatedness category "Definitely Related." A negative reaction to being observed would fit the study relatedness category "Possibly Related." as it will likely be difficult to precisely determine the origins of behaviors and reactions in residents with advanced dementia, and it is unclear the extent to which the resident might be aware that s/he is being observed. AEs resulting from negative reactions to the music are expected but likely rare. AEs resulting from negative reactions to the data collectors are not expected.

Serious Adverse Events: The potential serious adverse event (SAE) that could occur during this trial is a fall secondary to spontaneous ambulation (e.g., dancing) while listening to the music. Falls during spontaneous ambulation while listening to music could be classified as moderate or severe, depending on the presence of related injury and/or need for tertiary care. A fall during spontaneous ambulation while listening to the intervention, as this population of NH residents with moderate to severe dementia is prone to falls (independent of the intervention). This SAE is not expected, as falls are not consistent with available information about the intervention.

Unanticipated Problems: Unanticipated problems (UPs) are defined by DHHS 45 CFR part 46 as any incident, experience, or outcome that meets **all** of the following criteria:

- unexpected (in terms of nature, severity, or frequency) given (a) the research procedures that are described in the protocol-related documents, such as the IRB-approved research protocol and informed consent document; and (b) the characteristics of the study population;
- 2. related or possibly related to participation in the research (possibly related means there is a reasonable possibility that the incident, experience, or outcome may have been caused by the procedures involved in the research); and
- 3. suggests that the research places participants or others at a greater risk of harm (including physical, psychological, economic, or social harm) than was previously known or recognized.

Deaths: This study involves NH residents with advanced dementia. Death is expected in this population. In one of our ongoing, large cluster-randomized trials, which enrolls a similar population of NH residents with advanced dementia, we are observing a 60% annual mortality rate. There is no anticipated relationship whatsoever between the intervention (personalized music) and death.

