Table 1. Repeat Parallel Design

*Primary data collection conducted in Sequence 1 and Sequence 2 nursing homes during Period 1, and Sequence 2 and Sequence 3 nursing homes during Period 3

[figure not shown]
*Secondary data collection including Minimum Data Set (MDS) and medication order data collected in all periods for all sequences, even during the coronavirus.

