7.3. Followup for Serious Negative Reactions

Adverse Events, Serious Adverse Events, Unanticipated Problems, and Deaths have specific reporting procedures.

As part of NH staff training, instructions will be given as to what constitutes an AE / SAE / UP. NH staff will be instructed to stop the music if an event occurs in which resident distress seems to result from the music (AE). NH staff are already trained in fall response (SAE). The NH staff should report any AE / SAE / UP to his/her immediate supervisor as soon as possible, but not exceeding 4 hours after the event. If deemed by the supervisor to be a true AE / SAE / UP, the NH supervisor will complete a *Nursing Home Event Reporting Form*, which will be submitted to the research project director via email within 24 hours of the event. The project director will report the event to the PI via email or telephone immediately upon becoming aware of the event.

Similarly, as part of the observer training, data collectors will be given instructions as to what constitutes an AE / SAE / UP. Data collectors will be instructed to terminate an observation if an event occurs in which resident distress seems to result from being observed (AE). Data collectors will report events to the NH supervisor as soon as possible, but not exceeding 4 hours after the event. If deemed by the supervisor to be a true AE / SAE / UP, the NH supervisor will complete a *Nursing Home Event Reporting Form*, which will be submitted to the research project director via email within 24 hours of the event. The project director will report the event to the PI via email or telephone immediately upon becoming aware of the event.

Upon receipt of the *Nursing Home Event Reporting Form*, the project director and [name] will contact the NH supervisor and complete the *Event Verification Form*. [name] is a co-investigator on the project and a board-certified geriatrician with NH medical experience. Specifically, the project director and [name] will review the details of the event with the NH supervisor, confirm that the event meets criteria for a true AE / SAE / UP, and classify the severity, expectedness, and relatedness of the event.

During verification, if it is determined that the event does not meet the criteria for a true AE/ SAE/ UP, the *Nursing Home Event Reporting Form* and the *Event Verification Form* will be retained by the study team, and no further action will be taken.

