7.4. Protection Against Risks

Procedures to minimize against risks include: training NH staff on how to choose appropriate candidates to receive the intervention and how to deliver the intervention to minimize risk of negative reactions; training data collectors to conduct resident observations as unobtrusively as possible; and extensive data safety protocols.

Training NHs: There are several levels of ongoing training and monitoring. NH corporate leadership will receive a two-day initial training on how to help their participating NHs select residents who are likely to respond positively to the intervention. During this training, leadership will also be taught the best way to approach the residents with the music, in order to minimize negative reactions related to startling them. For example, the training details how to initially hold the headphones away from the resident's ears to allow the resident to hear and get used to the music before experiencing the sensory pressure of the headphones. Corporate leadership will then repeat this training with each of their participating NHs before the intervention begins. Once the intervention begins, monthly phone calls will be made to NH staff by corporate leadership and Brown University staff in order to reinforce these best practices for minimizing negative reactions and to monitor for any events that have not been otherwise reported. In addition, corporate leadership will visit each site twice during the study to make sure the intervention is being administered consistent with best practices.

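### Section 7.2 foresees falls only as a music-time SAE, and the protocol plans no comparison of falls between arms, although MDS data come from every home

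*Combined protocol and SAP*

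**What the plan says.** - **Named event (7.2).** "The potential serious adverse event (SAE) that could occur during this trial is a fall secondary to spontaneous ambulation". The sentence gives dancing as its example and limits the event to time spent with the music on.
- **Background risk (7.2).** The same paragraph says "this population of NH residents with moderate to severe dementia is prone to falls (independent of the intervention". It gives no rate, and it then classes the fall SAE as not expected.
- **How events are found (7.3, 7.4).** Staff are taught what to report: "As part of NH staff training, instructions will be given as to what constitutes an AE / SAE / UP". Corporate leaders give their training to the homes before the intervention starts. Calls that also look for unreported events follow: "Once the intervention begins, monthly phone calls will be made to NH staff by corporate leadership and Brown University staff". Data collectors are a further reporting route.
- **Who judges (7.3).** The nursing home supervisor screens each report. The project director and a co-investigator then classify severity, expectedness and relatedness case by case.
- **Outcomes and analysis (6, 9.4, Table 4, 9.5).** Falls are in none of them, and 9.5 contains no comparative safety analysis.
- **Deaths (Précis).** Deaths in both exposed and control residents go to the DSMB.
- **Data for both arms (Table 1 footnote).** "Secondary data collection including Minimum Data Set (MDS) and medication order data collected in all periods for all sequences". Section 6.1 describes the MDS content as including "continence, mood state, diagnoses, health conditions, special treatments, and medication use"; falls are not named.
- **Deferral (7.2).** The section opens by sending the reader to a Data Safety and Monitoring Plan and a DSMB Charter for the complete safety assessment.

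**The concern.** Falls are the one serious harm for which the protocol itself describes a mechanism: music prompts a resident to get up and move. The named event needs music, so its count in control homes is zero by definition and no risk difference or rate ratio can be formed from it. Residents fall for other reasons, so case-by-case relatedness judgements without a comparator cannot separate an excess from the background.

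At stake is what the trial may say about safety. A report of few related falls could be read as reassurance with nothing to compare it with, and a real excess could pass as background. Deaths, which the protocol does not expect the music to affect, get a two-population report; falls do not. Section 9.3 omits stopping rules partly because serious reactions are expected to be extremely rare, and nothing in the protocol checks that for falls by arm.

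**Working it through.** **1. What the named SAE covers.** Section 5.1 plans two sessions a day of 30 to 60 minutes, so 60 to 120 minutes. 60/1440 = 4.2% and 120/1440 = 8.3% of the day. Even in intervention homes, the named event leaves out more than 90% of the day.

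**2. Design inputs.** The only computable design figure is 24 homes per arm for the CMAI (9.2). With SD 20, difference 6, ICC 0.12, r = 0.5 and 15 residents per home (405/27 in Table 1):

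2 × (1.960 + 0.842)² × 20²/6² × (1 + 14 × 0.12) × (1 − 0.25) = 350.6 residents; 350.6/15 = 23.4, rounded up to 24. It reproduces. The documents give no fall rate, fall ICC or safety power.

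**3. What a two-arm comparison could deliver.** Inputs from the documents: 27 × 15 = 405 residents per arm. Assumptions: 8-month fall risk p of 30-50% and fall ICC of 0.01-0.05; ICC 0.12 is borrowed from the CMAI.

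SE = √[2p(1 − p)/405 × (1 + 14 × ICC)]

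| ICC | Design effect | SE at p = 0.3 / 0.5 | 95% half-width (1.96 × SE) | Difference with 80% power (2.80 × SE) |
|---|---|---|---|---|
| 0.01 | 1.14 | 3.44 / 3.75 | 6.7 / 7.3 points | 9.6 / 10.5 points |
| 0.05 | 1.70 | 4.20 / 4.58 | 8.2 / 9.0 points | 11.8 / 12.8 points |
| 0.12 | 2.68 | 5.27 / 5.75 | 10.3 / 11.3 points | 14.8 / 16.1 points |

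**4. Deaths.** Section 7.2 cites 60% annual mortality in a similar population. At a constant hazard, 0.40^(8/12) = 0.54 survive 8 months. If only survivors contribute, each arm has 405 × 0.54 = 218.7 residents, 8.1 per home. At ICC 0.12 the design effect is 1 + 7.1 × 0.12 = 1.85, the half-width 11.7 to 12.8 points, and the 80%-power difference 16.7 to 18.2 points. Person-time would recover part of this loss.

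**5. Session-only harm.** Assume a 30% background risk, falls spread evenly over 24 hours and full use of the music. A 10-point excess is an overall rate ratio of ln(0.60)/ln(0.70) = 1.43. If all of it arises during sessions, the in-session rate must rise by a factor of 1 + 0.43/0.083, about 6, with 2 hours a day, or 1 + 0.43/0.042, about 11, with 1 hour. Residents who are never given the music dilute it further. A whole-day comparison is therefore insensitive to a modest session-only harm.

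**The case against.** Two stronger readings are tempting, and the documents support neither.

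**That the trial cannot show whether the program increases falls.** Section 7.2 defers to a safety plan and charter that were not supplied, and a two-arm fall table could sit there. If the MDS extract holds falls, the trial could also answer the question with data it already receives. The gap is an unspecified analysis, not a design incapable of the comparison.

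**That falls are counted only in intervention homes.** This is an inference. The general adverse event definition in 7.2 covers any untoward occurrence, related or not, without limit by arm or music, and the fall is described as the potential SAE, that is, the one foreseen. Section 7.3 names no arm, and data collectors also report events; primary data come from control homes too. What remains is that nothing sets up systematic fall capture in controls. Visits are at baseline, 4 and 8 months, and 10.1 labels on-site collection as Trial 1 only. Any spontaneous reports would come from unequal ascertainment.

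Further objections hold in part:
- The sentence in 7.2 about residents being prone to falls is grammatically incomplete, perhaps through text extraction. The acknowledgement of a background risk is still legible.
- Section 6.1 lists health conditions among the MDS items but not falls, so the proposed source is an assumption.
- A null two-arm result could reassure falsely, as step 5 of the working shows. That argues for reporting an interval with its limits, not for having no comparator.
- The study is classed as minimal risk and the DSMB may ask for unblinding. Unblinding does not help if no comparable fall count exists for the control arm.

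**Conclusion.** The point holds in this form: the protocol defines its one foreseen SAE as a fall during music, ties staff training and monthly event calls to the intervention, and specifies no between-arm fall comparison, although it acknowledges a background risk and receives MDS data for all homes in all periods. Whether the safety plan or charter fills the gap is unknown.

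A two-arm comparison would give an estimate with a half-width of about 7-9 points at ICC 0.01-0.05 and about 10-11 points at ICC 0.12, wider after deaths. This rests on assumed fall risks of 30-50%, assumed fall ICCs (0.12 is the CMAI value) and 15 residents per home. It would show a large excess and leave a modest or session-only one open. The sponsor should act on it because the change affects what can be concluded about safety and costs little.

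**What to change.** 1. Check the Data Safety and Monitoring Plan and the DSMB Charter. If either specifies a both-arm fall comparison, cross-reference it in 7.2; items 2 to 4 then fall away.
2. Otherwise, confirm with the data manager that the health-condition items in the MDS extract include falls. Then add any fall, and fall with injury, from MDS assessments in each trial period as a safety outcome in 7.2 and 9.4.2.
3. Compare by randomised arm among all eligible residents, with clustering by home, person-time or another allowance for death, and a confidence interval. Put the two-arm table in the semi-annual DSMB report, starting with the completed first trial.
4. State the limits: the expected precision, that a null result does not exclude a modest or session-only increase, and that MDS falls may be under-recorded, possibly differently by arm if training changes recording.
5. Keep the event forms as they are. Reconcile the statements in 7.2 that residents are prone to falls and that the fall SAE is not expected, and check the incomplete sentence against the source file.

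Cost: one paragraph, one clustered model and one DSMB table. No new data collection is needed if falls are in the extract.
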